5. SAMPLE SIZE DETERMINATION

A two-stage study design was selected in order to minimize the number of study subjects treated if tipifarnib were considered not sufficiently efficacious to grant further development in this subject population. This design is intended to allow the termination of accrual in case of unacceptably low efficacy as measured by ORR and will be evaluated in a FAS basis.

In the first stage, 22 eligible subjects will be enrolled and randomized in to one of two dose regimen cohorts (11 subjects per cohort). If two or more responses are observed in a given dose regimen cohort, 7 additional study subjects will be enrolled. Each dose regimen cohort is designed to test the null hypothesis of ORR rate less than 10% vs alternative hypothesis of ORR rate at least 30% and will be evaluated independently. At the completion of the study, treatment will be considered of further interest if 4 or more subjects in the 18 subject dose regimen cohort achieve a response, i.e. the true ORR is higher than 10%.

To determine the total trial size, a response of interest of 30% is assumed. This design provides 80% power to detect a difference between 10% and 30% red blood cell (RBC) transfusion independence (TI) rate at one-sided significance level of 0.087. Using this design, the probability of terminating each stratum at the end of stage 1 if the true rate is 10% is 0.697 while the probability of terminating each stratum at the end of stage 1 if the true rate is 30% is 0.113.

The performance characteristics of this approach are shown in Table 3.

Table 2: Performance characteristics for sample size determination

		Probability to conclude TRUE rate > 0.10 if TRUE underlying RBC TI response rate is as indicated		
TRUE Rate -->		0.1	0.3	0.4
TRUE Rate -->	N=11	0.09	0.69	0.88
TRUE Rate -->	N=18	0.1	0.83	0.97
TRUE Rate -->	N=25	0.1	0.91	0.99
TRUE Rate -->	N=32	0.09	0.95	>0.99

6. ANALYSIS POPULATIONS

Full Analysis Set (FAS)

The full analysis set (FAS) will serve as the primary population for the analysis of ORR and other efficacy-related data. Prior to Protocol Amendment 3 (version 09 Jul 2017), other subjects were enrolled into the trial using a different dose regimen. Also, for inclusion in the FAS, subjects must meet all Protocol Amendment 3 inclusion criteria. For the purposes of the primary analysis (advancement from stage 1 to stage 2 and overall analysis for each dose regimen

cohort), those subjects will not be included. The excluded subject data will be summarized separately in the reporting of the study.

Therefore, subjects will be excluded for FAS for the following reasons:

- Did not meet eligibility criteria as outlined in Protocol Amendment 3 (version 09 Jul 2017)
- Failure to receive at least one dose of tipifarnib
- No post-baseline endpoint data subsequent to at least 1 dose of study drug.
- Enrolled prior to Protocol Amendment 3 (version 09 Jul 2017)

Per-Protocol (PP) Population

A supportive analysis may be performed on the PP population which excludes subjects due to important deviations from the protocol that may substantially affect the results of the primary analysis, such as not taking at least 80% of the intended dose in cycle 1. The final determination on protocol violations, and thereby the composition of the PP population, will be made prior to locking the clinical database and final analysis and will be documented in a separate memorandum.

All Subjects as Treated (ASaT) Population

The ASaT population will be used for the analysis of safety data. The ASaT population consists of all enrolled subjects who receive at least one dose of tipifarnib. At least one laboratory or vital sign measurement obtained subsequent to at least one dose of study drug is required for inclusion in the analysis of a specific safety parameter. To assess change from baseline, a baseline measurement is also required.

7. GENERAL STATISTICAL CONSIDERATIONS

7.1. Interim Analyses and Data Monitoring

Based on the two-stage trial design, an interim analysis will be conducted to determine advancement from Stage 1 to Stage 2. Specifically, according to the Protocol, Section 8.1, if 2 responses are observed during Stage 1, then 7 additional subjects will be enrolled in Stage 2. If 0-1 objective responses are observed, the study will be closed to further reenrollment. No statistical hypothesis will be tested for this analysis.

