8 TRIAL DESIGN

8.1 Study Design

This phase 2 study will investigate the antitumor activity in terms of ORR of tipifarnib in approximately 36 eligible subjects with MDS who have no known curative treatment.

A two-stage study design was selected in order to minimize the number of study subjects treated if tipifarnib were considered not sufficiently efficacious to grant further development in this subject population. This design is intended to allow the termination of accrual in case of unacceptably low efficacy as measured by ORR.

In the first stage, 22 eligible subjects will be enrolled and randomized in to one of two dose regimen cohorts (11 subjects per cohort). If two or more responses are observed in a given dose regimen cohort, 7 additional study subjects will be enrolled. Each dose regimen cohort is designed to test the null hypothesis of ORR rate less than 10% vs alternative hypothesis of ORR rate at least 30% and will be evaluated independently. At the completion of the study, treatment will be considered of further interest if the true ORR rate is higher than 10% (at least 4

responders out of 18 subjects in a dose regimen cohort). This design provides 80% power to detect a difference between 10% and 30% ORR rate at one-sided significance level of 0.087.

Only consented subjects who meet all eligibility criteria will be enrolled in the study. Screening evaluations will be completed within 4 weeks (28 days) of Cycle 1 Day 1. Any screening evaluation, including disease status, will need to be repeated if performed more than 4 weeks from Cycle 1 Day 1. Evaluations performed as part of the standard of care within 28 days of dosing but prior to consent, do not need to be repeated. By signing the consent form, study subjects agree to the collection of standard of care health information.

Subjects will be randomized to receive tipifarnib orally with food, twice a day (bid) according to one of the following dose regimens:

• Regimen 1: 600 mg bid for 7 days on Days 1-7 in 28 day cycles (i.e. 1 week on / 3 weeks off).

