12.2 Endpoints

12.2.1 Efficacy

Disease response assessment will be performed by the Investigator according to the MDS IWG criteria (Table 9 and Table 10).

For the evaluation of the primary endpoint (i.e. ORR) to determine advancement to the second stage of the study (i.e. enrollment of 7 additional subjects in the dose regimen cohort) and overall outcome of the study, each dose regimen cohort will be evaluated independently.

Transfusion independence and disease response will be summarized descriptively per dose regimen cohort and overall.

The objective response rate will be estimated and includes the following response types: CR, PR, marrow CR and HI according to the MDS IWG criteria (Table 9 and Table 10). The estimate of the objective response rate will be calculated based on the maximum likelihood estimator (i.e., crude proportion of subjects whose best overall response is CR, PR, marrow CR or HI). The estimate of the objective response rate will be accompanied by 2-sided 95% exact binomial confidence intervals.

The duration of objective response will be calculated for subjects who achieve CR, PR, marrow CR or HI. For such subjects, the duration of objective response is defined as the number of days from the start date of response (whichever response is achieved first) to the first date that progressive disease is objectively documented. Disease progression will be determined by the Investigator using MDS IWG criteria (Table 10). The duration of objective response will be right-censored for subjects who achieve a response and meet 1 of the following conditions: 1) non-protocol anticancer treatment started before documentation of disease progression, 2) death or documented disease progression after more than 1 missed disease assessment visit, or 3) alive and does not have documentation of disease progression before a data analysis cutoff date.

The duration of objective response will be summarized descriptively using the Kaplan-Meier method. The 50th percentile of the Kaplan-Meier distribution will be used to estimate the median response duration.

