13. DATA HANDLING CONVENTIONS

Analyses will be performed using SAS® [SAS Institute 2011] Version 9.3 or higher.

The clinical database will be locked prior to the initiation of the Stage 1 statistical analyses. A database lock is defined as a stable database that can be analyzed and reported. Changes to a locked database must be authorized in writing by the study sponsor [REDACTED]

The data conventions include the following.

- Data will be described and summarized by study stage (Stage 1 or Stage 2), Stage 1 cohort (starting dose level and schedule), or Stage 2 cohort (disease type).
- Summary tables for continuous variables will contain the following statistics: N (number of subjects in the population); n (number of subjects with data for that variable); mean; standard deviation; median; minimum; and maximum. Selected statistics may also include 2 sided 95% normal approximation confidence intervals (CI) on the mean.
- Summary tables for categorical variables will include: N (number of subjects in the denominator); n (number of subjects in the numerator); and percent. Selected statistics also may include 2-sided 95% CIs for the percent, calculated using the CL=AGRESTICOULL option in SAS PROC FREQ.

- The baseline value for a given parameter is the last value prior to the first dose. A value is considered to be post-baseline if it is obtained after the first dose. A value is considered to be postdose on a given cycle day if it is obtained after the dose is administered on that day.
- Data from all study centers will be pooled for all analyses.
- Unless otherwise specified, statistical testing will be 2-sided at a nominal 0.05 level of significance.
- Study day is defined as calendar date – date of first treatment + 1 if the calendar date is on or after the date of first treatment, and calendar date – date of first treatment if the calendar date is before the date of first treatment
- Measurements from unscheduled visits will be included in listings, but not summary tables.
- Missing data conventions for individual endpoints are described in the SAP section for the endpoint.
- Additional exploratory analyses may be performed as deemed appropriate after review of the pre-specified analyses. Log-transformations or nonparametric tests may be applied to measurements displaying a significant degree of non-normality.
- Listings will be provided for all data collected in the eCRF.

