15. CHANGES IN THE STATISTICAL METHODS FROM THOSE STATED IN THE PROTOCOL

None.

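### SAP 7.1 restates the Stage 1 stop/go rule without the dose regimen cohort and closes the whole study, contradicting the per-cohort rule behind the stated operating characteristics

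*SAP*

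**What the plan says.** Protocol 8.1 sets the rule by cohort: "If two or more responses are observed in a given dose regimen cohort, 7 additional study subjects will be enrolled". Stage 1 has 22 subjects, 11 per regimen. Protocol 12.2.1 confirms that, for advancement and for the final outcome, "each dose regimen cohort will be evaluated independently". SAP 4.1 and SAP 5 repeat the per-cohort condition, and SAP 5 gives its properties by cohort: "the probability of terminating each stratum at the end of stage 1 if the true rate is 10% is 0.697", with 0.113 at 30%. SAP 6 also speaks of "advancement from stage 1 to stage 2 and overall analysis for each dose regimen" cohort.

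SAP 7.1, the section on the interim analysis, says that it follows Protocol 8.1. Its wording is different: "if 2 responses are observed during Stage 1, then 7 additional subjects will be enrolled in Stage 2", and then "If 0-1 objective responses are observed, the study will be closed to further reenrollment". SAP 15, headed "CHANGES IN THE STATISTICAL METHODS FROM THOSE STATED IN THE PROTOCOL", has the single entry None.

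**The concern.** SAP 7.1 departs from the rule it cites in three ways. It does not name the unit in which responses are counted, it writes 2 where the protocol has two or more, and at 0-1 responses it closes the study rather than the cohort. The first and third matter most. With two randomized regimens, a rule without a unit can be read literally in two ways:

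- **Reading A:** the 22 Stage 1 subjects are counted together, and 0-1 responses in total closes the study.
- **Reading B:** each cohort is counted separately, but 0-1 responses in either one closes the study.

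The two err in opposite directions. Reading A lets an inactive regimen continue on the other's responses. Reading B lets an inactive regimen stop an active one. SAP 7.1 is also the only place in the SAP that states what is done at 0-1 responses, so someone carrying out the Stage 1 analysis would turn to it. At stake is the trial's one adaptive decision.

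**Working it through.** **Inputs.** Stage 1: 11 subjects per cohort. Stage 2: 7 more. Continue at 2 or more of 11; success at 4 or more of 18; null rate 10%, alternative 30% (Protocol 8.1, SAP 5). Stated results: early stop 0.697 and 0.113, alpha 0.087, power 80%.

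**1. Per-cohort rule (reproduces the plan).** Early stop = P(X ≤ 1 of 11).

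- At 10%: 0.9^11 + 11 × 0.1 × 0.9^10 = 0.3138 + 0.3835 = 0.6974.
- At 30%: 0.7^11 + 11 × 0.3 × 0.7^10 = 0.0198 + 0.0932 = 0.1130.

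Success = sum over x ≥ 2 of P(X1 = x) × P(X2 ≥ 4 − x), with X2 out of 7.

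- At 10%: 0.2131 × 0.1497 + 0.0710 × 0.5217 + 0.0185 = 0.0875 (0.08749 before rounding, printed in the plan as 0.087).
- At 30%: 0.1998 × 0.6706 + 0.2568 × 0.9176 + 0.4304 = 0.800.

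All four stated figures are reproduced.

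**2. Reading A: one pooled count, stop at 0-1 of 22.**

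- Both regimens at 10%: 0.9^22 + 22 × 0.1 × 0.9^21 = 0.0985 + 0.2407 = 0.339.
- One at 10%, the other at 30%: 0.3138 × 0.0198 + 0.3835 × 0.0198 + 0.3138 × 0.0932 = 0.043.

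If both cohorts then expand to 18, a 10% regimen's false-go probability gains the paths in which it had 0 or 1 response itself but the pooled count passed:

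- Other regimen at 10%: 0.0875 + 0.3835 × 0.6862 × 0.0257 + 0.3138 × 0.3026 × 0.0027 = 0.0945.
- Other regimen at 30%: 0.0875 + 0.3835 × 0.9802 × 0.0257 + 0.3138 × 0.8870 × 0.0027 = 0.0979.

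Expected total sample size depends on how SAP 7.1's 7 additional subjects are read:

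| True rates | Per-cohort rule | Pooled, 7 more in all | Pooled, 7 more in each cohort |
|---|---|---|---|
| 10% / 10% | 22 + 14 × 0.3026 = 26.2 | 22 + 7 × 0.6608 = 26.6 | 22 + 14 × 0.6608 = 31.3 |
| 10% / 30% | 22 + 7 × 0.3026 + 7 × 0.8870 = 30.3 | 22 + 7 × 0.9570 = 28.7 | 22 + 14 × 0.9570 = 35.4 |

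The false-go figures belong with the last column, because both cohorts reach 18 only there.

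**3. Reading B: 0-1 of 11 in either cohort closes the study.** For a 30% regimen:

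| Other regimen | Passes its own gate but is closed | Power |
|---|---|---|
| 10% | 0.8870 × 0.6974 = 0.619 | 0.8001 × (1 − 0.6974) = 0.242 |
| 30% | 0.8870 × 0.1130 = 0.100 | 0.8001 × 0.8870 = 0.710 |

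**4. The word 2 read as exactly 2.** P(X = 2 of 11) is 0.213 at 10% and 0.200 at 30%. Outcomes of 3 or more (0.090 and 0.687) would then have no rule. The paired 0-1 clause makes this reading implausible.

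**The case against.** The strongest reply is that the documents settle the matter. SAP 7.1 sends the reader to Protocol 8.1, and the per-cohort rule stands there, in Protocol 12.2.1, and in SAP 4.1, 5 and 6. On this view SAP 7.1 is a loose paraphrase and needs only an editorial correction. That is right about the intent, and it is why the point is not a design failure. It does not make SAP 7.1 correct: the section gives a different rule under the protocol's name, and no clause says which SAP section prevails.

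Four narrower objections have some force:

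- Writing 2 for two or more is minor, since the 0-1 clause implies the complement. The substance is the missing cohort and the closing of the study.
- Reading B takes cohort counting from Protocol 8.1 but not the independent evaluation stated in the same section. Its largest effect also needs one regimen at 10% and the other at 30%, which the documents give no reason to expect. It is a conditional worst case.
- Under Reading A the rise in false-go is small. The main loss is early stopping; with a single 7 added, expected sample size hardly moves.
- A reference to the full analysis set (FAS) in the corrected sentence comes from SAP 5, not Protocol 8.1. That is so, but SAP 5 already puts the two-stage evaluation on that basis, so nothing new is introduced.

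**Conclusion.** The concern holds. SAP 7.1 contradicts the rule it cites, and SAP 15 declares no change that could explain it. The stated 0.697, 0.113, 0.087 and 80% belong to the per-cohort rule.

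- **Pooled reading:** the early-stopping probability of a 10% regimen drops from 0.697 to 0.339 or 0.043, and false-go rises from 0.0875 to at most 0.0979 if both cohorts expand.
- **Either-cohort reading:** power for a 30% regimen drops from 0.800 to 0.710 when the other regimen is also at 30%, and to 0.242 when the other is at 10%.

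These figures assume independent binomial responses, full cohorts of 11 and 18, and SAP 7.1 applied literally. If the team applies the protocol's rule, nothing is lost. This is an internal contradiction in a decision rule that should be corrected before the Stage 1 analysis.

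**What to change.** Rewrite the rule in SAP 7.1 by cohort, for example:

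*The Stage 1 decision is made separately for each dose regimen, on the FAS basis given in Section 5. A cohort with at least 2 responders among its 11 Stage 1 subjects enrolls 7 more subjects. A cohort with 0 or 1 responder is closed to enrollment, and this has no effect on the other cohort.*

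A separate, minor clean-up: SAP 13 labels Stage 2 cohorts by disease type, which does not fit this design. The label should be dose regimen cohort.

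The cost is one restated rule and one corrected label in the SAP. The protocol, sample size, error rates and response counting are unchanged, because the edit restores the rule from which the plan's figures were computed.

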7.2. Multi-Center Studies

This is a multi-center study. Given the small sample size of the study, no site effect will be considered in any statistical analysis.

7.3. Multiple Comparisons / Multiplicity

Given the small sample size, no adjustment for multiple comparisons/multiplicity will be performed. Therefore, only nominal p-values will be reported.

7.4. Examination of Subgroups

No sub-group analyses are planned.

7.5. Handling of Dropouts or Missing Data

Where individual data points are missing because of insufficient samples, dropouts, or other reasons, the data will be analyzed based on reduced denominators. For survival analysis, dropouts without confirming events will be treated as censored.

7.6. Outlier Handling

Potential data entry errors manifested as outliers will be handled in the data management process through edit checks.

7.7. Adjustments for Covariates

Not applicable.

8. SUMMARY OF STUDY POPULATION DATA

Unless specifically noted, all tables, listings, and figures described will not include subjects enrolled prior to Protocol Amendment 3.

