12.2.2 Safety and Tolerability

Safety and tolerability of tipifarnib will be assessed based on the following:

- Incidence, duration, and severity of TEAEs, SAEs, AEs resulting in permanent discontinuation of study drug, and deaths within approximately 30 days from the last dose of study drug (or immediately before the administration of another anticancer treatment)
- Changes in laboratory test results

AEs will be coded using the latest available version of the Medical Dictionary for Regulatory Activities (MedDRA). TEAEs are defined as AEs that start on or after the first dose of study

drug and within approximately 30 days of the last administration of study drug. AEs will be summarized by the number and percentage of subjects who experienced the event, according to system organ class and preferred term. A subject reporting multiple cases of the same AE will be counted once within each system organ class and similarly counted once within each preferred term

Unless specified otherwise, the denominator for these calculations will be based on the number of subjects in each cohort who received at least one administration of tipifarnib, irrespective of the total number of doses or treatment cycles administered. These conventions will be appropriately modified to calculate AE incidence rates separately for each cycle that study therapy is administered. AE incidence rates may also be calculated based on other measures of subject exposure (e.g., total number of treatment cycles administered). AEs will also be summarized by NCI CTCAE v.4.03 severity grade, by relationship to each study drug and by treatment regimen. Additional summaries may also be provided for SAEs, and events resulting in the permanent discontinuation of therapy. All AEs will be included in individual subject listings.

The incidence of grade 3 and 4 hematological toxicities (including neutropenia, thrombocytopenia, and anemia) will be provided by treatment cycle and across all treatment cycles. The toxicity grades for laboratory tests will be based on NCI CTCAE v.4.03 criteria. The use of blood transfusions (platelets, red blood cells, whole blood) and/or growth factor support will be reported.

Vital sign results (heart rate, blood pressure and temperature) will be summarized descriptively for each scheduled and unscheduled protocol time point. Changes will be calculated relative to the assessments at baseline.

Sample Size Determination

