Subjects who received a starting dose of 900 mg bid during the conduct of the original version of this protocol may be dose reduced to the 600 mg bid dose at the discretion of the investigator (protocol Amendment 1). Subjects who received tipifarnib on Days 1 – 7 and Days 15 – 21 during the conduct of the original version and amendment 1 of this protocol, may transition to

the new treatment administration schedule (tipifarnib on Days 1-7 in 28 day cycles) beginning on Day 1 of their next cycle.

Subjects accrued prior to Protocol Amendment 3, 09 July 2017, will not be included in the total disposition and were not considered in the sample size determination detailed in section 5 of this SAP. The estimated number of 36 subjects enrolled do not include these subjects. For analysis, this subject population will only be included in the Total Adverse Event tables.

In the absence of unmanageable toxicities, subjects may continue to receive tipifarnib treatment until disease progression. If a complete response (CR) is observed, therapy with tipifarnib will be maintained for at least 6 months beyond the start of response.

Hematologic assessments, including peripheral blood evaluations and review of transfusion requirements, will be performed at screening and at least monthly until disease progression. Disease assessments will also be performed at screening and at least once every approximately 12 weeks starting at the end of cycle 3. As part of the disease assessment at screening and during Cycles 3, 6 and 9, bone marrow evaluation will be performed. Thereafter, bone marrow evaluations will occur during disease assessments in accordance with institutional standard practice. Additional hematologic or disease assessments may be conducted if deemed necessary by the Investigator. The timing of the hematologic and disease assessments should be maintained as much as possible independently of potential treatment cycle delays.

Determination of ORR will be assessed by the Investigator according to the MDS International Working Group (IWG) criteria (Table 8 and Table 9 in the study protocol).

Upon disease progression, all subjects in the study will be followed approximately every 12 weeks for survival and the use of subsequent therapy until either death or 12 months after accrual of the study has been completed, whichever occurs first. Information on survival and subsequent anticancer therapy may be collected by phone.

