10. SAFETY ANALYSES

Safety and tolerability of tipifarnib will be assessed based on the following:

- Incidence, duration and severity of TEAEs, SAEs, AEs resulting in permanent discontinuation of study drug, and deaths within approximately 30 days from the last dose of study drug (or immediately before the administration of another anti-cancer treatment)
- Changes in laboratory test results
- Serum Chemistry: Blood Urea Nitrogen, Creatinine, Potassium, Calcium, Total Bilirubin, ALT, AST
- Hematology: White Blood Cell Count, Hemoglobin, Platelet Count, Absolute Neutrophil Count, Neutrophil Precursors (promyelocytes, myelocytes, metamyelocytes, band neutrophils), Lymphocytes, Monocytes, Blasts, and Reticulocytes.
- Coagulation panel: PT/INR, APTT
- Changes in vital signs: blood pressure, heart rate, temperature

Unless explicitly indicated otherwise, all analyses for safety will be based on the ASaT population.

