10.1. Adverse Events

Adverse events will be coded using the latest available version of the Medical Dictionary for Regulatory Activities (MedDRA). Treatment-emergent adverse events are defined as AEs that start on or after the first dose of study drug and within approximately 30 days of the last administration of study drug. AEs will be summarized by the number and percentage of subjects who experienced the event, according to SOC and PT. A subject reporting multiple cases of the same AE will be counted once within each SOC and similarly counted once within each PT. For summaries by maximum severity, each subject will be counted only once under the most severe event.

Unless specified otherwise, the denominator for these calculations will be based on the number of subjects who received at least one administration of tipifarnib regardless of the total number of doses or treatment cycles administered. These conventions will be appropriately modified to calculate AE incidence rates separately for each cycle that study therapy is administered. AE incidence rates may also be calculated based on other measures of subject exposure (e.g., total number of treatment cycles administered). For subjects enrolled prior to Protocol Amendment 3, their AE counts will only be provided in the Total column (Regimen 1 + Regimen 2 + Original Cohort). Regimen 1 and Regimen 2 subjects will be presented separately and in the Total columns.

AE durations will be calculated using all TEAEs. For any AE that is still ongoing at the end of study, we will use the last contact date as the end of AE stop date for calculation the duration of AEs. Median, minimum and maximum of AE durations will be reported.

AEs will also be summarized by NCI-CTCAE version 4.03 severity grade and by relationship to each study drug. Additional summaries may also be provided for SAEs, and events resulting in the permanent discontinuation of therapy. All AEs will be included in individual subject listings.

Hematologic abnormalities reported as AEs that were coded to preferred terms in the Investigations SOC have been pooled with appropriate terms in the Blood and Lymphatic System SOC for tabulation for the following categories:

- Platelet count decreased = Thrombocytopenia;
- Neutrophil count decreased = Neutropenia;
- White blood cell count decreased = Leukopenia;
- Lymphocyte count decreased = Lymphopenia.

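### Treated subjects enrolled before Amendment 3 get no separate safety summary and drop out of the laboratory, transfusion, vital-sign and exposure summaries, although the SAP's safety population includes them

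*SAP*

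**What the plan says.** The safety population has no enrolment cut-off. SAP 6 states: "The ASaT population consists of all enrolled subjects who receive at least one dose of tipifarnib". Protocol 12.1.2 defines it in the same way, and SAP 10 adds: "Unless explicitly indicated otherwise, all analyses for safety will be based on the ASaT population".

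Three other places restrict subjects enrolled before Amendment 3 (09 Jul 2017):

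- SAP 4.1: "For analysis, this subject population will only be included in the Total Adverse Event tables".
- SAP 8, with a reservation for anything specifically noted: "all tables, listings, and figures described will not include subjects enrolled prior to Protocol Amendment 3".
- SAP 10.1, on the adverse event tables: "their AE counts will only be provided in the Total column (Regimen 1 + Regimen 2 + Original Cohort").

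Of the subjects left out of the full analysis set (FAS), SAP 6 and Protocol 12.1.1 both say: "The excluded subject data will be summarized separately in the reporting of the study". Protocol 12.2.2 requires adverse events to be summarised "by relationship to each study drug and by treatment regimen". SAP 15 lists no departures from the protocol.

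On listings, SAP 10.1 undertakes to list every adverse event by subject, and SAP 13 undertakes to list everything collected on the eCRF.

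**The concern.** An efficacy exclusion appears to have been carried over into safety. Changed eligibility or dosing can justify leaving earlier subjects out of a response rate. It does not by itself justify leaving dosed subjects out of safety summaries, and the SAP gives no reason for doing so.

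Myelosuppression is the toxicity most at stake. According to Protocol 9.4, it was the reason the alternate-week schedule was dropped in Amendment 2, after the first 9 subjects were reviewed. Protocol 10.4 keeps abnormal laboratory findings out of adverse event reporting unless they come with signs or symptoms, lead to discontinuation or are judged medically important. An asymptomatic severe cytopenia may therefore show only in the laboratory tables, from which these subjects are absent. Protocol 9.4 also says the study's data will be used to choose a dose and regimen, so safety data by schedule bear on that choice.

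**Working it through.** The point rests mainly on comparing the texts. The plan gives no figure to reproduce.

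**Step 1: which outputs lose these subjects.**

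- Adverse events (SAP 10.1): included, but only within the pooled Total.
- Exposure and compliance (SAP 8.4): excluded by SAP 8 and by SAP 4.1.
- Grade 3 or higher hematological toxicity and the shift table (SAP 10.2), transfusion and growth factor support (SAP 10.3), and vital signs (SAP 10.4): these lie outside SAP 8, so the exclusion rests on SAP 4.1. None of these sections brings the subjects back.
- Baseline tables labelled ASaT (SAP 8.3): excluded by SAP 8. The same population label would then carry a smaller number here than in the adverse event Total.
- Separate summary of excluded subjects: promised in SAP 6, but no later section describes one.
- Listings: excluded by SAP 4.1 and SAP 8, included by SAP 10.1 and SAP 13. The SAP contradicts itself.

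**Step 2: how many subjects.** Inputs: at least 9 subjects on the earlier schedule (Protocol 9.4, taking all 9 as dosed); 36 planned later subjects (Protocol synopsis); 22 if both cohorts stop after stage 1. Share = earlier / (earlier + later).

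- 9 / (9 + 36) = 9/45 = 20%.
- 9 / (9 + 22) = 9/31 = 29%.

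Nine is a minimum, because the total enrolled before Amendment 3 is not given. With an assumed 20 earlier subjects, the shares are 20/56 = 36% and 20/42 = 48%.

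**Step 3: what the pooled Total mixes.** Nominal dose per full 28-day cycle = dose x 2 x dosing days.

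- 900 mg bid, Days 1-7 and 15-21: 900 x 2 x 14 = 25,200 mg.
- 600 mg bid, same days: 600 x 2 x 14 = 16,800 mg.
- Regimen 1: 600 x 2 x 7 = 8,400 mg.
- Regimen 2: 300 x 2 x 21 = 12,600 mg.

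The spread is up to 25,200 / 8,400 = 3.0-fold. To illustrate the dilution, assume an event rate of 60% in 9 earlier subjects and 20% in 36 later ones. The Total column would show (0.6 x 9 + 0.2 x 36) / 45 = 12.6/45 = 28%, which describes neither group.

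**Step 4: what subtraction recovers.** Total minus Regimen 1 minus Regimen 2 gives the earlier group's crude adverse event counts. It does not give median event durations (SAP 10.1), laboratory shifts, transfusion use or exposure, and it cannot split the earlier group by dose or schedule.

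**Step 5: who is in the earlier group.** Protocol 9.4 places the start of both current schedules in Amendment 2 (20 Dec 2016), more than six months before Amendment 3. Anyone enrolled in between would have started Regimen 1 or 2, yet SAP 10.1 would count that person only in the Total. SAP 6 says those enrolled before Amendment 3 had a different dose regimen, which would not fit such a subject. Neither document says whether there were any.

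**The case against.** The strongest reply is that the SAP made a deliberate exception. SAP 10 allows explicit departures from ASaT, and SAP 4.1 and 10.1 can be read as such departures. The sentence in SAP 8 carries a reservation and opens the study-population section, so it may govern that section alone. The promise of a separate summary sits in the FAS paragraph and does not name safety data. Table layouts are in a companion shells document that is not available here. Amendment 3 changed the neutrophil and platelet entry criteria, so mixing earlier subjects into the current regimen columns would combine different baseline blood counts. The primary endpoint and the two-stage decision are unaffected.

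Much of this stands. It makes the conflict with ASaT a matter of unreconciled wording more than an outright prohibition, it makes SAP 4.1 the firmer basis for the point, and it argues for keeping earlier subjects visibly apart. It does not explain why they should have no separate display, or why SAP 15 reports no change.

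A reader might go further and infer that toxicity on the most intensive dosing is never shown. The documents do not support that. Crude counts can be derived, and SAP 10.1 and SAP 13 promise listings. The group is also not simply the 900 mg bid subjects: it includes 600 mg bid on alternate weeks, in unstated proportions, and Protocol 9.4 attributes the poor recovery to the schedule. Nor can it be stated as fact that Regimen 1 and 2 rates will omit subjects who received those regimens, because enrolment between Amendments 2 and 3 is possible but undocumented.

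**Conclusion.** The concern holds as a conflict within the SAP and between the SAP and the protocol. Followed as written, the plan gives treated subjects enrolled before Amendment 3 no safety summary of their own and omits them from every summary of laboratory toxicity, transfusion, vital signs and exposure. The affected group is at least 9 subjects, about 20% of those treated if 36 later subjects enrol and 29% if only 22 do. These shares assume that the 9 reviewed subjects were all dosed and that no others were enrolled before Amendment 3. Any further early enrolment raises them. What is lost is separate and laboratory-based safety information. Efficacy conclusions are not affected.

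**What to change.** Before the database is frozen, amend the SAP as follows.

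- In SAP 4.1 and 8, limit the pre-Amendment 3 exclusion to efficacy (FAS) outputs.
- Base adverse event, laboratory, transfusion, vital-sign and exposure summaries on the full ASaT, with columns for Regimen 1, Regimen 2, Original Cohort (alternate-week schedule) and Total. Bring SAP 10.1 into line.
- Show any subject who started Regimen 1 or 2 under Amendment 2 by the regimen received, flagged or in a sub-column because Amendment 3 changed the blood-count criteria.
- State the number of subjects in each of these groups, including how many started at 900 mg bid.
- Confirm in SAP 8, 10.1 and 13 that listings cover every dosed subject.
- If any exclusion from safety summaries is kept, give the reason and record it in SAP 15.

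The cost is revised wording and extra columns across the safety tables, some with very few subjects. No new data are needed.
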